14. Contraindications to or hypersensitivity to drugs used in the study including but not limited to fexofenadine, loratadine, desloratadine, cetirizine, levocetirizine, rupatadine, epinephrine or any of their ingredients.
15. Documented history of anaphylaxis including exercise induced anaphylaxis (not related to anaphylactoid-like reaction associated with CINDU).
16. History of malignancy of any organ system within the past 5 years (except for basal cell carcinoma or actinic keratoses or Bowen disease (carcinoma in situ) that have been treated, with no evidence of recurrence in the past 12 weeks; carcinoma in situ of the cervix or non-invasive malignant colon polyps that have been removed).
17. Presence of clinically significant cardiovascular (such as but not limited to myocardial infarction, unstable ischemic heart disease, NYHA Class III/IV left ventricular failure, arrhythmia and uncontrolled hypertension within 12 months prior to screening visit (Visit 1)), neurological, psychiatric, metabolic or other pathological conditions (such as but not limited to cerebrovascular disease, neurodegenerative or other neurological diseases, uncontrolled hypo- and hyperthyroidism and other autoimmune diseases, hypokalemia, hyperadrenergic state or ophthalmologic disorder) that could interfere with or compromise the safety of the participants, interfere with evaluation or interpretation of the study results, or preclude completion of the study.
18. Medical examination or laboratory findings that suggest the possibility of decompensation of co-existing conditions for the duration of the study. Any items that are cause for uncertainty will be reviewed with the investigator.
19. Participants with history of HIV (Human immunodeficiency virus) infection.
20. Participants with evidence of or history of chronic hepatitis B virus (HBV) infection and/or hepatitis C virus (HCV) infection.
21. History of, or current treatment for, hepatic disease including but not limited to cirrhosis or hepatic failure or AST (aspartate aminotransferase)/ALT (alanine aminotransferase)/albumin/TBL (total bilirubin )/ levels of more than 1.5x upper limit of normal (ULN) at screening visit (Visit 1).
22. History of renal disease or creatinine level above 1.5x ULN at screening visit (Visit 1).
23. Platelets < 100 000/ $\mu$ L at screening visit (Visit 1).

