## 16.2 Appendix 2: Liver event and laboratory trigger definitions & follow-up requirements

**Table 16-3 Liver event and laboratory trigger definitions**

	Definition/ threshold
Liver laboratory triggers If ALT, AST and total bilirubin normal at baseline:	
 
• ALT or AST > 5 × ULN
 
• ALP > 2 × ULN (in the absence of known bone pathology)
 
• Total bilirubin > 3 × ULN (in the absence of known Gilbert syndrome)
 
• ALT or AST > 3 × ULN and INR > 1.5
 
• Potential Hy's Law cases (defined as ALT or AST > 3 × ULN and Total bilirubin > 2 × ULN [mainly conjugated fraction] without notable increase in ALP to > 2 × ULN)
 
• Any clinical event of jaundice (or equivalent term)
 
• ALT or AST > 3 × ULN accompanied by (general) malaise, fatigue, abdominal pain, nausea, or vomiting, or rash with eosinophilia
 
• Any adverse event potentially indicative of a liver toxicity*
 

If ALT or AST abnormal at baseline:	ALT or AST > 3x baseline or > 300 U/L (whichever occurs first)
*These events cover the following: hepatic failure, fibrosis and cirrhosis, and other liver damage-related conditions; non-infectious hepatitis; benign, malignant and unspecified liver neoplasms ULN: upper limit of normal	

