**Table 16-4 Follow up requirements for liver laboratory triggers – ALT, AST, TBL**

	ALT	TBL	Liver Symptoms	Action
ALT increase without bilirubin increase:				
	If normal at baseline: ALT > 3 x ULN  If elevated at baseline: ALT > 2 x baseline or > 300 U/L (whichever occurs first)	Normal For participants with Gilbert's syndrome: No change in baseline TBL	None	
 
• No change to study treatment
 
• Measure ALT, AST, ALP, GGT, TBIL, INR, albumin, CK, and GLDH in 48-72 hours.
 
• Follow-up for symptoms.
 

	ALT	TBL	Liver Symptoms	Action	
	
If normal at baseline: ALT > 5 x ULN for more than two weeks
 
If elevated at baseline: ALT > 3 x baseline or > 300 U/L (whichever occurs first) for more than two weeks
	
Normal
 
For participants with Gilbert's syndrome: No change in baseline TBL
	None	
 
• Interrupt study drug
 
• Measure ALT, AST, ALP, GGT, TBIL, INR, albumin, CK, and GLDH in 48-72 hours.
 
• Follow-up for symptoms.
 
• Initiate close monitoring and workup for competing etiologies.
 
• Study drug can be restarted only if another etiology is identified and liver enzymes return to baseline.
 
	
	
If normal at baseline: ALT > 8 x ULN
	Normal	None		
ALT increase with bilirubin increase:					
	
If normal at baseline: ALT > 3 x ULN
 
If elevated at baseline: ALT > 2 x baseline or > 300 U/L (whichever occurs first)
	
TBL > 2 x ULN (or INR > 1.5)
 
For participants with Gilbert's syndrome: Doubling of direct bilirubin
	None		
	
If normal at baseline: ALT > 3 x ULN
 
If elevated at baseline: ALT > 2 x baseline or > 300 U/L (whichever occurs first)
	Normal or elevated	Severe fatigue, nausea, vomiting, right upper quadrant pain		

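### Table 16-4 has no row for an asymptomatic ALT rise with bilirubin above 1 and up to 2 × ULN, so mandatory interruption lapses at ALT >5 × ULN for over two weeks

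*Protocol*

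**What the plan says.** Appendix 2 (Section 16.2) of the protocol holds three tables.

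- **Table 16-3** defines the liver triggers. The first list is headed "Liver laboratory triggers If ALT, AST and total bilirubin normal at baseline". The second is for participants whose ALT or AST was abnormal at baseline.
- **Table 16-4** gives the actions for ALT rises. The asymptomatic rows for ALT >3 × ULN and for ALT >5 × ULN lasting more than two weeks carry the bilirubin condition "Normal For participants with Gilbert's syndrome: No change in baseline TBL"; the ALT >8 × ULN row requires normal bilirubin with no Gilbert's clause. Beside the two-week row the action is "Interrupt study drug", with the restart rule "Study drug can be restarted only if another etiology is identified and liver enzymes return to baseline". The combined row needs TBL >2 × ULN or INR >1.5 (with Gilbert's syndrome, "Doubling of direct bilirubin"). The last row accepts any bilirubin but requires symptoms: "Severe fatigue, nausea, vomiting, right upper quadrant pain".
- **Table 16-5** covers isolated bilirubin rises. At >1.5 to 3.0 × ULN it keeps treatment going and asks for repeat tests in 48–72 hours.

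For every Table 16-3 event, Section 10.2.1 asks for repeat chemistry with no deadline and, once the rise is confirmed, close observation in which interruption is considered. Discontinuation and hospitalisation follow if appropriate.

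**The concern.** The rows leave a band of bilirubin values between them. A participant with persistent ALT >5 × ULN and normal bilirubin must have the drug interrupted. If bilirubin also rises modestly, to no more than 2 × ULN, no row applies and interruption is no longer mandatory. Yet that participant is closer to the Hy's Law threshold in Table 16-3 (ALT or AST >3 × ULN with TBL >2 × ULN). The required action becomes weaker as the liver picture gets worse. What is at stake is consistent handling across sites of a rare but important safety case.

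**Working it through.** **Inputs.** Row conditions of Table 16-4, for a participant with normal baseline ALT and no Gilbert's syndrome:

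| Row | ALT | TBL / INR | Symptoms | Drug action in the text |
|---|---|---|---|---|
| 1 | >3 × ULN | TBL normal | none | no change |
| 2 | >5 × ULN, over two weeks | TBL normal | none | interrupt |
| 3 | >8 × ULN | TBL normal | none | cell blank |
| 4 | >3 × ULN | TBL >2 × ULN or INR >1.5 | none | cell blank |
| 5 | >3 × ULN | any | required | cell blank |

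**Step 1, coverage.** With no symptoms and INR ≤1.5, the rows accept TBL ≤1 × ULN or TBL >2 × ULN. What remains is 1 < TBL ≤ 2 × ULN.

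**Step 2, enumeration.** The rows were coded and run over ALT 4, 6, 9 and 15 × ULN; duration up to or over two weeks; TBL 0.9, 1.0, 1.2, 1.6, 2.0 and 2.1 × ULN; and INR 1.0 and 1.6. That is 4 × 2 × 6 × 2 = 96 cases. No row applies in 4 × 2 × 3 × 1 = 24 of them: every case with TBL 1.2, 1.6 or 2.0 and INR 1.0. All other cases match at least one row.

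**Step 3, what is lost (INR 1.0).**

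| ALT, duration | TBL ≤1 × ULN | TBL 1.2–2.0 × ULN | Drug action lost? |
|---|---|---|---|
| 4 × ULN, any | row 1 | no row, no numeric Table 16-3 trigger | no |
| 6 × ULN, up to two weeks | row 1 | no row; Table 16-3 trigger | no |
| 6 × ULN, over two weeks | rows 1 and 2 | no row; Table 16-3 trigger | **yes** |
| 9 or 15 × ULN, up to two weeks | rows 1 and 3 | no row; Table 16-3 trigger | only if the action cell is merged |
| 9 or 15 × ULN, over two weeks | rows 1, 2 and 3 | no row; Table 16-3 trigger | **yes** |

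Where no drug action is lost, the prompt panel of row 1 still is: "Measure ALT, AST, ALP, GGT, TBIL, INR, albumin, CK, and GLDH in 48-72 hours". The Section 10.2.1 repeat names six tests against nine here, and sets no time limit.

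**Step 4, Gilbert's syndrome.** TBL changed from baseline without doubled direct bilirubin also falls between the rows.

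**Step 5, baseline bilirubin.** Exclusion criterion 21 removes "levels of more than 1.5x upper limit of normal (ULN) at screening visit (Visit 1", so TBL >1 to 1.5 × ULN is admissible unless another criterion applies. A participant with that TBL and normal ALT and AST fits neither Table 16-3 list: the first needs all three normal, the second needs ALT or AST abnormal. Read literally, even the ALT >5 × ULN trigger that leads to Section 10.2.1 is then unclear.

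**Step 6, doses at stake.** Doses fall on Days 1, 29, 57, 85, 113 and 141. No chemistry row is visible in Table 8-1, so the day of detection is an assumption. If chemistry is drawn at every dosing visit and ALT >5 × ULN is found on Day 29 and persists, the two-week condition is met by Day 29 + 15 = 44, leaving 4 later doses (Days 57, 85, 113, 141). Found on Day 141, it leaves 0. If chemistry follows the visible dipstick timing (Weeks 12, 24 and 36), detection on Day 85 leaves 2. The range of 0 to 4 reflects these assumptions and is not an estimate.

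**The case against.** The strongest reply is that the participant is not unprotected. Section 10.2.1 brings repeat tests, observation and consideration of interruption. Section 9.1.1 goes further: it requires discontinuation for adverse events where continued exposure would be detrimental, and wherever participation might pose a safety risk. A clinically significant laboratory value counts as an adverse event. If the event is reported as a liver-toxicity adverse event, the last row of Table 16-5 asks the site to consider stopping. The central laboratory flags out-of-range values, and a sensible investigator would treat the band at least as strictly as normal bilirubin.

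All of this stands, and it keeps the point small. It does not close the gap. The Section 9.1.1 requirements bind only once the investigator judges them met, its liver-specific bullet points back to Appendix 2, and Section 10.2.1 refers to Tables 16-4 and 16-5 for the detailed actions.

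A reader might also infer more than the text supports:

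- *Action is weaker throughout the band.* It is not: at ALT >3 × ULN, and at >5 to 8 × ULN for up to two weeks, normal bilirubin also means no change to treatment.
- *Table 16-5 orders treatment to continue.* Its bilirubin rows are for isolated rises. A site would have to misapply them.
- *The whole combination can be present at entry.* Only the bilirubin part can; criterion 21 also excludes ALT above 1.5 × ULN.

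**Conclusion.** The gap holds on the literal text. For an asymptomatic participant without Gilbert's syndrome, ALT >3 × ULN with TBL above ULN up to 2 × ULN and INR ≤1.5 has no row in Table 16-4. The loss of a mandatory drug action is confined to ALT >5 × ULN for more than two weeks, plus ALT >8 × ULN if the blank action cells are one merged cell, which the extracted text cannot settle. There, interruption and the restricted restart give way to investigator judgement.

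The size cannot be fixed. The documents give no incidence, and a firm count of doses at stake would need a chemistry schedule that is not visible. Hepatotoxicity is not among the treatment risks summarised in Section 4.5. No endpoint or analysis is touched. The SAP records termination with 39 participants enrolled and treatment stopped, so the point concerns the plan as written and any protocol that reuses these tables. Severity: minor; a cheap improvement.

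**What to change.** - **Table 16-4, three asymptomatic ALT rows:** replace the normal-bilirubin condition with *not meeting the combined row (TBL ≤2 × ULN and INR ≤1.5; for Gilbert's syndrome, direct bilirubin not doubled)*, and reword the heading above them to match.
- **Raised TBL below the interruption rows:** for any ALT >3 × ULN with TBL above ULN that does not meet the >5 × ULN two-week row or the >8 × ULN row, write *consider interruption* and keep the 48–72 hour panel. Without this, the first change would place such participants under an instruction to leave treatment unchanged.
- **AST:** change ALT to *ALT or AST* in the Table 16-4 rows. Table 16-3 triggers on either enzyme, so an asymptomatic AST-only trigger would otherwise still have no row, and full coverage could not be claimed.
- **Overlap:** state that the stricter action applies where Tables 16-4 and 16-5 both describe a case.
- **Table 16-3:** head the first list *If ALT and AST normal at baseline*, so that it covers participants admitted with TBL up to 1.5 × ULN.

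The cost is wording edits to two appendix tables and one added sentence, with a few extra liver panels or interruptions. Endpoints, sample size and analyses are unaffected.

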**Table 16-5 Follow up requirements for liver events and laboratory triggers – Isolated Hyperbilirubinemia**

Criteria	Actions required	Follow-up monitoring
Total Bilirubin (isolated)		
>1.5 – 3.0 ULN	
 
• Maintain treatment
 
• Repeat LFTs within 48-72 hours
 
	Monitor LFTs weekly until resolution to ≤ Grade 1 or to baseline
> 3 - 10 × ULN (in the absence of known Gilbert syndrome)	
 
• Interrupt treatment
 
• Repeat LFT within 48-72 hours
 
• Hospitalize if clinically appropriate
 
• Establish causality
 
• Record the AE and contributing factors (e.g. conmeds, med hx, lab) in the appropriate CRF
 
	
Monitor LFTs weekly until resolution to ≤ Grade 1 or to baseline (ALT, AST, total bilirubin, Alb, PT/INR, ALP and GGT)
 
Test for hemolysis (e.g. reticulocytes, haptoglobin, unconjugated [indirect] bilirubin)

> 10 x ULN	
 
• Discontinue the study treatment immediately
 
• Hospitalize the participant
 
• Establish causality
 
• Record the AE and contributing factors(e.g. conmeds, med hx, lab)in the appropriate CRF
 
	ALT, AST, TBL, Alb, PT/INR, ALP and GGT until resolution (frequency at investigator discretion)
Any AE potentially indicative of a liver toxicity*	
 
• Consider study treatment interruption or discontinuation
 
• Hospitalization if clinically appropriate
 
• Establish causality
 
• Record the AE and contributing factors(e.g., conmeds, med hx, lab)in the appropriate CRF
 
	Investigator discretion

\*These events cover the following: hepatic failure, fibrosis and cirrhosis, and other liver damage – related conditions; non-infectious hepatitis; the benign, malignant and unspecified liver neoplasms.

Based on investigator’s discretion investigation(s) for contributing factors for the liver event can include: Serology tests, imaging and pathology assessments, hepatologist’s consultancy; obtaining more detailed history of symptoms and prior or concurrent diseases, history of concomitant drug use, exclusion of underlying liver disease.

### 16.3 Appendix 3: Specific Renal Alert Criteria and Actions and Event Follow-up

**Table 16-6 Specific renal alert criteria and actions**

Renal Event	Actions
Confirmed serum creatinine increase 25% - 49%	
 
· Consider causes and possible interventions
 
· Follow up within 2-5 days
 

Serum creatinine increase $\geq 50\%$ * OR if <18 years old, eGFR < 35mL/min/1.73 m 	
 
· Consider causes and possible interventions
 
· Repeat assessment within 24-48h if possible
 
· Consider drug interruption or discontinuation unless other causes are diagnosed and corrected
 
· Consider patient hospitalization and specialized treatment
 

New onset dipstick* proteinuria $\geq 3+$ OR Protein-creatinine ratio (PCR) $\geq 1\text{g/g Cr}$ (or mg/mmol equivalent as converted by the measuring laboratory)	
 
· Consider causes and possible interventions
 
· Assess serum albumin & serum protein
 
· Repeat assessment to confirm
 
· Consider drug interruption or discontinuation unless other causes are diagnosed and corrected
 

New onset hematuria $\geq 3+$ on urine dipstick*	
 
· Assess & document
 
· Repeat assessment to confirm
 
· Distinguish hemoglobinuria from hematuria
 
· Urine sediment microscopy
 
· Assess SCR
 
· Exclude infection, trauma, bleeding from the distal urinary tract/bladder, menstruation
 
· Consider bleeding disorder
 

* Corresponds to KDIGO (Kidney Disease Improving Global Outcomes) criteria for Acute Kidney Injury                      * For point of care tests (POCT), the clinical sites in China will be allowed to analyze these tests as per clinical site practice (refer to China laboratory manual for further details)
	

Whenever a renal event is identified, a detailed patient history and examination are indicated to identify and potentially eliminate risk factors that may have initiated or contributed to the event:

- Blood pressure assessment (after 5-minute rest, with an appropriate cuff size)
- Signs and symptoms like fever, headache, shortness of breath, back or abdominal pain, dysuria or hematuria, dependent or periorbital edema
- Changes in blood pressure, body weight, fluid intake, voiding pattern, or urine output
- Concomitant events or procedures such as trauma, surgical procedures, cardiac or hepatic failure, contrast media or other known nephrotoxin administration, or other diseases or causes, e.g., dehydration due to delirium, tumor lysis

**Table 16-7 Renal event follow-up**

Follow-up of renal events

1. Assess, document and record in CRF
 
 
• Urine dipstick* and sediment microscopy evidence of drug induced nephrotoxicity: crystals, red blood cells (dysmorphic/glomerular vs. non-dysmorphic/non-glomerular), white blood cells, tubular epithelial cells
 
• Blood pressure and body weight
 

#### Follow-up of renal events

- Serum creatinine, BUN, electrolytes (sodium, potassium, phosphate, calcium), bicarbonate and uric acid
  - Urine output
2. Review and record possible contributing factors to the renal event (co-medications, other co-morbid conditions) and additional diagnostic procedures (Magnetic Resonance Imaging etc.) in the CRF
  3. Monitor patient regularly (frequency at investigator's discretion) until -
    - Event resolution: (SCR within 10% of baseline or protein-creatinine ratio < 1 g/g Cr, or ACR <300 mg/g Cr of baseline) or
    - Event stabilization: SCR level with  $\pm 10\%$  variability over last 6 months or protein-creatinine ratio stabilization at a new level with  $\pm 50\%$  variability over last 6 months
  4. Analysis of urine markers in samples collected over the course of the drug induced nephrotoxicity event

\*For point of care tests (POCT), the clinical sites in China will be allowed to analyze these tests as per clinical site practice (refer to China laboratory manual for further details)

## 16.4 Appendix 4 Sampson Criteria for anaphylaxis

**Anaphylaxis is highly likely when any one of the following 3 criteria are fulfilled:**

1. Acute onset of an illness (minutes to several hours) with involvement of the skin, mucosal tissue, or both (eg, generalized hives, pruritus or flushing, swollen lips-tongue-uvula)  
*AND AT LEAST ONE OF THE FOLLOWING*
  - a. Respiratory compromise (eg, dyspnea, wheeze-bronchospasm, stridor, reduced PEF, hypoxemia)
  - b. Reduced BP or associated symptoms of end-organ dysfunction (eg, hypotonia [collapse], syncope, incontinence)
2. Two or more of the following that occur rapidly after exposure to a *likely allergen for that patient* (minutes to several hours):
  - a. Involvement of the skin-mucosal tissue (eg, generalized hives, itch-flush, swollen lips-tongue-uvula)
  - b. Respiratory compromise (eg, dyspnea, wheeze-bronchospasm, stridor, reduced PEF, hypoxemia)
  - c. Reduced BP or associated symptoms (eg, hypotonia [collapse], syncope, incontinence)
  - d. Persistent gastrointestinal symptoms (eg, crampy abdominal pain, vomiting)
3. Reduced BP after exposure to *known allergen for that patient* (minutes to several hours):
  - a. Infants and children: low systolic BP (age specific) or greater than 30% decrease in systolic BP\*
  - b. Adults: systolic BP of less than 90 mm Hg or greater than 30% decrease from that person's baseline

[figure not shown]
PEF, Peak expiratory flow; BP, blood pressure.

[figure not shown]
\*Low systolic blood pressure for children is defined as less than 70 mm Hg from 1 month to 1 year, less than  $(70 \text{ mm Hg} + [2 \times \text{age}])$  from 1 to 10 years, and less than 90 mm Hg from 11 to 17 years.

[figure not shown]

[REDACTED]

[figure not shown]
[REDACTED]

[figure not shown]

[figure not shown]

[figure not shown]

[figure not shown]

[figure not shown]

[figure not shown]

[figure not shown]

[figure not shown]

## 16.7 Appendix 7: World allergy organization grading system

**Figure 16-1 World allergy organization subcutaneous immunotherapy systemic reaction grading system**

Grading system for SARs				
Grade 1	Grade 2	Grade 3	Grade 4	Grade 5
			Anaphylaxis	

Symptom(s)/sign(s) from 1 organ system present
 
Cutaneous
 
 
• Urticaria and/or erythema-warmth and/or pruritus, other than localized at the injection site
 
• And/or
 
• Tingling, or itching of the lips* or
 
• Angioedema (not laryngeal)*
 
 
Or
 
Upper respiratory
 
 
• Nasal symptoms (eg, sneezing, rhinorea, nasal pruritus, and/or nasal congestion)
 
• And/or
 
• Throat-clearing (itchy throat)*
 
• And/or
 
• Cough not related to bronchospasm
 
 
Or
 
Conjunctival
 
 
• Erythema, pruritus, or tearing
 
 
Or
 
Other
 
 
• Nausea
 
• Metallic taste
 
	
Symptom(s)/sign(s) from <math>\geq 2</math> organ symptoms listed in grade 1
	
Lower airway
 
 
• Mild bronchospasm, eg, cough, wheezing, shortness of breath which responds to treatment
 
• And/or
 
 
Gastrointestinal
 
 
• Abdominal cramps* and/or vomiting/diarrhea
 
 
Other
 
 
• Uterine cramps
 
• Any symptom(s)/sign(s) from grade 1 would be included
 
	
Lower airway
 
 
• Severe bronchospasm, eg, not responding or worsening in spite of treatment
 
• And/or
 
 
Upper airway
 
 
• Laryngeal edema with stridor
 
• Any symptom(s)/sign(s) from grades 1 or 3 would be included
 
	
Lower or upper airway
 
 
• Respiratory failure and/or
 
 
Cardiovascular
 
 
• Collapse/hypotension†
 
• And/or
 
• Loss of consciousness (vasovagal excluded)
 
• Any symptom(s)/sign(s) from grades 1, 3, or 4 would be included
 

Due to the early termination of the trial, screening was stopped and all subjects in treatment where discontinued, therefore the trial has a limited sample size. No statistical analyses will be performed on any dataset. Summarization of the data will be limited to data listings and summary tables where necessary Sections of the SAP are written as per protocol, language was added at the end of each section to address the termination of the study. Below are specific, high level changes to the SAP and subsequent output:

- Screening was stopped and all subjects in treatment where discontinued
- No statistical analyses will be performed on the primary endpoints
- No statistical analyses will be performed on the secondary endpoints

█

- No interim analysis will be performed
- No summary tables will be produced for efficacy

█

